6.3.9 Concomitant Medications

All concomitant medications/therapies will be summarised as number of patients being treated with each type of medication/therapy classified according to ATC level 3 group text and World Health Organization (WHO) Drug Dictionary preferred name.

Prior medication/therapy is defined as medication/therapy administered prior to Screening Visit. All medication/therapy administered after Screening Visit are considered concomitant medication/therapy. Prior medication/therapy will be indicated as past or ongoing at Screening.

In summary tables, each patient is only counted once for each drug, on a preferred name level and will be classified according to the first start date of the medication. If there is an occurrence of the same preferred name before and after screening, the medication is only counted as started before screening. For total within each group text, a patient can be counted both before and after screening if one medication is present at screening, and another medication with another preferred name starts after baseline.

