12.1.11 Concomitant Treatment

Concomitant medication and concomitant therapy will be summarized as number of patients being treated with each type of medication/therapy classified according to ATC level 3 and WHO Drug Dictionary preferred term. The safety set will be used for this presentation.

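### A drug restarted after Screening is tabulated only as started before it, so the after-Screening count in the concomitant medication table is a lower bound on on-study use

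*SAP*

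**What the plan says.** SAP section 6.3.9 sets two definitions, both based on when a drug was given. For prior use: "Prior medication/therapy is defined as medication/therapy administered prior to Screening Visit". For concomitant use: "All medication/therapy administered after Screening Visit are considered concomitant medication/therapy". Protocol section 10.4.4 defines the two terms in the same way. The SAP adds a status marker for prior drugs: "Prior medication/therapy will be indicated as past or ongoing at Screening".

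For the summary table the basis changes from administration to start date: "each patient is only counted once for each drug, on a preferred name level and will be classified according to the first start date". The case of repeated use is then settled explicitly: "If there is an occurrence of the same preferred name before and after screening, the medication is only counted as started before screening". At ATC group level, "a patient can be counted both before and after screening if one medication is present at screening" and a drug with a different preferred name starts later.

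Protocol section 12.1.11 describes the same summary without a before/after split. Medication is to be "summarized as number of patients being treated with each type of medication/therapy", in the safety set. SAP Appendix 1 plans one such table (14.3.8.2) and a patient listing (16.2.11.1).

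**The concern.** A concomitant medication table should let the reader see how many patients received a given drug during the trial. Under the rule in 6.3.9, a patient who used a drug in the month before Screening, stopped it and took it again on study appears only in the started-before category. The later use is concomitant by the SAP's own definition but leaves no trace in the after-Screening count.

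The started-before category cannot be used to put this right. It combines drugs ongoing at Screening with drugs stopped and restarted, and also drugs used only in the past if those are tabulated. The past/ongoing marker has no value for a restart.

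What is at stake is the readability of one descriptive safety table. Drugs taken intermittently are the most exposed. Antipyretics are a plausible example, because Protocol section 5.1 reports transient fever and rash in 5 of 12 patients in the first study and only one arm here is vaccinated. Section 6.3.9 itself names no drug.

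**Working it through.** The documents state no figure for this count, so there is nothing to reproduce. The check has two parts: reading the rules against each other, and simple count arithmetic.

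**Reading.** Take one patient and one preferred name.

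| Pattern of use | Concomitant by definition? | Category in the table |
|---|---|---|
| Past only | No | Before, if tabulated at all |
| Ongoing at Screening and continued | Yes | Before |
| Stopped, then restarted after Screening | Yes | Before |
| First used after Screening | Yes | After |

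Only the last row reaches the after-Screening count. At ATC level, a patient in the third row is added to the after-Screening total only if a different drug in the group also starts later. ATC-level before and after counts can also overlap, so their sum is not a number of patients.

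**Arithmetic.** Let S be the number of on-study users of a drug, and B the number of those who also have an earlier record of it. The after-Screening count is S − B, so the relative shortfall is B/S. This needs no assumption.

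To illustrate, assume that a share p has an earlier record, that a share q uses the drug on study, and that the two are independent. None of these values is in the documents. Then, in an arm of n patients:

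- on-study users: n·q
- after-Screening count: n·q·(1 − p), a relative shortfall of p
- before-Screening count, with past-only drugs tabulated: n·p
- before plus after: n·(p + q − p·q)

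About 90 patients at 2:1 gives about 60 in the vaccine arm. With n = 60 and q = 0.40, on-study users are 60 × 0.40 = 24.

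| p | After-Screening count | Before count | Sum |
|---|---|---|---|
| 0 | 24.0 | 0 | 24.0 |
| 0.1 | 21.6 | 6.0 | 27.6 |
| 0.3 | 16.8 | 18.0 | 34.8 |
| 0.5 | 12.0 | 30.0 | 42.0 |

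For p = 0.3, the before count of 18 consists of 60 × 0.3 × 0.4 = 7.2 on-study users and 60 × 0.3 × 0.6 = 10.8 past-only users. The true 24 lies between the after-Screening count (16.8) and the sum (34.8), and the table does not say where. If past-only drugs are left out, the before count is 7.2 and the sum is 7.2 + 16.8 = 24, which is correct at preferred-name level. The SAP does not say which applies.

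A comparison between arms is affected in the same way. If p = 0.3 in both arms and true use is 60% against 40%, the after-Screening counts show 60 × 0.7 = 42% against 40 × 0.7 = 28%, so a difference of 20 points appears as 14.

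**The case against.** The strongest reply is that this is a display convention and nothing is lost. The category label refers to when the drug started. A drug ongoing at Screening also started before it and is still concomitant, so showing it there is correct. The prior and concomitant definitions can both apply to one drug, and Protocol 12.1.11 promises no before/after split that the SAP could breach. Every on-study user is somewhere in the table, and each record, with dates, indication and any adverse event reference, is collected under Protocol 10.4.4 and listed.

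Most of this stands, and it rules out three stronger readings that a reader might infer:

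- **That restarted drugs are reclassified as prior and drop out of the table.** The text says started before, and the patient remains counted.
- **That the SAP contradicts its own definition.** The definitions overlap. The fault is that the table's categories do not follow them.
- **That the rule would hide a breach of the oral steroid restriction in Protocol section 9.6.** The table carries no dose and no cut-off at nephrectomy, so it could not show a breach under any counting rule. SAP section 5 handles prohibited medication through review of protocol deviations before database lock.

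Vaccine reactions are likewise captured as adverse events, with a separate summary for the four hours after vaccination.

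What the reply does not answer is that the number of patients treated on study cannot be read from the table when past-only drugs are tabulated. The after-Screening count is then too low and the sum too high. At ATC level the overlap of the two counts remains even if past-only drugs are left out.

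**Conclusion.** The concern holds as a minor defect of tabulation. The direction follows from the text alone: any on-study user with an earlier record of the same drug is missing from the after-Screening count, which is therefore a lower bound. For drugs ongoing at Screening, the past/ongoing marker could recover the number if it were tabulated. For restarted drugs it could not.

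The size cannot be known from the documents. Under independence the relative shortfall equals the share with earlier recorded use, which is 0% to 50% over the range shown. Where earlier and later use go together, B/S exceeds that share. All usage rates above are assumptions.

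The effect is confined to one descriptive table in the safety set. No endpoint, test or analysis set draws on it, and listing 16.2.11.1 keeps the individual records.

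**What to change.** In SAP section 6.3.9, replace the rule for repeated use. Count a patient as a concomitant user of a drug if it was administered at any time after the Screening Visit, and as a prior user if it was administered before it. Allow the same patient to appear in both, at preferred-name and ATC level. Then show three groups separately: past only, ongoing at Screening, and newly started or restarted after Screening.

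The start and end dates needed are already collected under Protocol section 10.4.4, so no new data are required. The cost is a short text change and minor reprogramming of one table. The downside is that the prior and concomitant columns are no longer mutually exclusive and cannot be added, which a footnote should state.

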6.3.10 Adverse Events

Analyses of AEs will be based on the Safety set. AEs will be coded using Medical Dictionary for Regulatory Activities (MedDRA) Version 17.1.

All AEs will be listed by treatment group, with patient number in addition to type of event (verbatim term, system organ class and preferred term), start and stop day relative to first dose of treatment, seriousness, intensity, action taken, relationship to study drug and outcome of AE. Treatment-emergent status will be flagged in the listing. In addition, corresponding listings of screening AEs, serious AEs (SAEs), AEs leading to discontinuation of study medication, AEs leading to death will be produced.

The total number of AEs will be summarized including the number of patients with at least one AE, the total number of AEs, the number of unique AEs, by seriousness, intensity, action taken, relationship to study drug and by treatment group and in total. The number of AEs per severity (CTCAE) and relation to trial drug will also be included and summarized per treatment group and in total. SAEs will also be summarized separately in a similar manner.

The number of patients and the number of AEs will be tabulated by MedDRA system organ class (SOC) and preferred term in descending order of overall frequency.

AEs occurring during the 4 hours following the Intuvax vaccination will in addition be summarized separately.

Summary statistics of AE will be done by treatment group.

Pre treatment events occurring between first assessment at Screening and first Intuvax dose (for vaccinated patients) and between first assessment at Screening and Nephrectomy (for unvaccinated patients) will be summarized separately.

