7.2.1.2 Vacc1 Visit (if applicable)

This visit is applicable only for patients randomized to Intuvax followed by sunitinib.

TIME WINDOW:

Vacc1 Visit to be done within 28 days after Screening

ACTIVITIES AND ASSESSMENTS:

Day before vaccination (optional):

The following assessments may be done the day before vaccination for logistical reasons:

- Laboratory Safety Blood Assessments: Hematology, Clinical Chemistry, PT-INR, and APTT, *Section 10.5.5*
- Pregnancy (either blood or urine), *Section 10.5.5*
- Laboratory Safety Urine Assessments, *Section 10.5.5*
- Physical Examination, *Section 10.5.3*
- ECOG performance status, *Section 10.2.3.1*
- AEs, *Section 11.2*

Day of vaccination (Pre-Vaccination):

NB: Absolute fasting for four (4) h prior to Intuvax administration applies.

- Concomitant Medication, *Section 10.4.4*
- Physical Examination unless done the day before, *Section 10.5.3*
- Vital Signs, *Section 10.5.4*
- Laboratory Safety Blood Assessments: Hematology, Clinical Chemistry, PT-INR, and APTT unless done the day before, *Section 10.5.5*
- Pregnancy (either blood or urine test) unless done the day before, *Section 10.5.5*
- Laboratory Safety Urine Assessments unless done the day before, *Section 10.5.5*
- Auto- and alloimmunization (baseline), *Section 10.5.6.1* and *Section 10.5.6.2*
- ECOG performance status unless done the day before, *Section 10.2.3.1*
- AEs, *Section 11.2*

Day of vaccination (Vaccination)

- Injection of Intuvax into the viable part of the renal tumor using CT or Ultrasound monitoring for confirmation of administration location, *Section 9.1.5*

Day of vaccination (Post-Vaccination)

- Vital Signs, *Section 10.5.4*
- AEs, *Section 11.2*
- Concomitant Medication, *Section 10.4.4*

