7.2.1.3 Vacc2 Visit (If applicable)

This visit is applicable only for patients randomized to Intuvax followed by sunitinib.

TIME WINDOW:

14 days (± 3 days) after Vacc1 Visit

ACTIVITIES AND ASSESSMENTS

Exactly the same activities and assessments will be done at this visit as was done on Vacc1 Visit except for auto- and alloimmunization, *Section 7.2.1.2*.

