12.1.12 Adverse Events

Analyses of AEs will be based on the Safety set. AEs will be coded using MedDRA.

The total number of AEs will be summarized including the number of patients with at least one (1) AE, the total number of AEs, the number of unique AEs per treatment group and in total. The number of AEs per severity (CTCAE) and relation to trial drug will also be included and summarized per treatment group and in total. SAEs will be summarized in a similar manner.

The number of patients and the number of AEs will be tabulated by MedDRA system organ class and preferred term. AEs will also be tabulated versus worst severity and worst relationship to treatment. In this table, patients with AEs will be identified by their patient number.

AEs occurring during the 4 hours following the Intuvax vaccination will in addition be summarized separately.

Pretreatment events occurring between first assessment at Screening and first Intuvax dose (for vaccinated patients) and between first assessment at Screening and Nephrectomy (for unvaccinated patients) will in addition be summarized separately.

All AEs summaries will be made overall and separately by stratum.

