6.6 Handling of Dropouts and Missing Data

Primary and secondary efficacy endpoint

The primary and secondary efficacy endpoint analysis will be conducted on available data (observed cases). Missing data due to loss of follow-up and rules for censoring will be done as described in each corresponding section.

Handling of incomplete dates

Incomplete (partial or missing) dates will be presented in data listings as provided on the eCRF. However, for use in calculations (e.g. to calculate the duration of an AE or medication use) dates will be estimated as follows.

For partial start-dates

- If the year is unknown, then the date will not be imputed and will be assigned a missing value
- If the month is unknown, then:
 - If the year matches the year of the first dose date, then impute the month and day of the first dose date
 - Otherwise, assign 'January'
- If the day is unknown, then:
 - If the month and year match the month and year of the first dose date, then impute the day of the first dose date.
 - Otherwise, assign 'January'.

For partial end-dates,

- If the year is unknown, then the date will not be imputed and will be assigned a missing value.
- If the month is unknown, then assign 'December'.
- If the day is unknown, then assign the last day of the month

If the above rules for end-dates result in a date after the patient was ended the study, then the end date will be replaced with the patient's date of completion/withdrawal. Furthermore, should the above rules not result in the most conservative date (as described below), then the imputed value may be replaced by a date that will lead to a more conservative analysis.

After implementing the rules above, to determine whether AEs with incomplete start or stop dates are pre-treatment or treatment-emergent the following strategy will be used:

- If the start date and stop date are both missing, the most conservative approach is taken and the AE is considered to be treatment-emergent
- If the start date is missing but the stop date is not missing and is on or after the day of first study drug administration but before or on the Week 12 visit date then the most conservative approach is taken and the AE is considered to be treatment-emergent;
- If the start date is missing but the stop date is not missing and is before the day of first study drug administration then the AE is considered to be pre-treatment.

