14.3.1 Displays of Adverse Events

- 14.3.1.1 Summary of Adverse Events
- 14.3.1.2 Summary of Adverse Events by ilixadencel batch subgroup
- 14.3.1.3 Adverse Events by System Organ Class and Preferred term
- 14.3.1.4 Adverse Events: Number of Patients by Intensity and Relationship by Treatment
- 14.3.1.5 Adverse Events: Number of Patients by Intensity and Relationship by Treatment by ilixadencel batch subgroup
- 14.3.1.6 Serious Adverse Events by System Organ Class and Preferred term
- 14.3.1.7 Related Adverse Events by System Organ Class and Preferred term
- 14.3.1.8 Adverse Events by CTCAE grade and System Organ Class and Preferred term
- 14.3.1.9 Adverse Events occurring 4 hours following the Intuvax vaccination
- 14.3.1.10 Adverse Events occurring between first assessment at Screening and first Intuvax dose
- 14.3.1.11 Adverse Events occurring between first assessment at Screening and Nephrectomy
- 14.2.1.12 Related Serious Adverse Events by System Organ Class and Preferred term

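### The period-based AE summaries use different cut-offs by arm, a second cut-off conflicts with them for controls, and AEs are reported as counts with no time denominator

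*SAP*

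**What the plan says.** SAP 6.3.10 defines the pre-treatment summary separately by arm. For the vaccine arm it covers "Pre treatment events occurring between first assessment at Screening and first Intuvax dose (for vaccinated patients". For controls it covers events "between first assessment at Screening and Nephrectomy (for unvaccinated patients) will be summarized separately". Protocol 12.1.12 has the same split and makes clear that this summary is an extra: "and between first assessment at Screening and Nephrectomy (for unvaccinated patients) will in addition be summarized separately". SAP Appendix 1 keeps two tables: 14.3.1.10 stops at the first Intuvax dose, and 14.3.1.11 is titled "Adverse Events occurring between first assessment at Screening and Nephrectomy".

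SAP 6.6 has another milestone, for AEs whose dates are incomplete. If the start is missing and the stop date "is before the day of first study drug administration then the AE is considered to be pre-treatment". SAP 6.3.10 also says that treatment-emergent status will be flagged in the listing and that AE days will be counted from first dose, but it does not define treatment-emergent for AEs with complete dates.

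The planned measure is a count: "The number of patients and the number of AEs will be tabulated by MedDRA system organ class" and preferred term. No rate per unit of time is planned. AEs are recorded from Screening to the End-of-Study Visit (Protocol 10.5.2), and progression turns the current visit into the End-of-Study Visit (Protocol 7.2.1.6).

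**The concern.** Safety in vaccinated and non-vaccinated patients is the first secondary objective listed in the protocol and the SAP, so a reader will set the arms side by side. The two periods of most interest are the one after vaccination and before surgery, and the one after surgery and before sunitinib. Neither has a table that covers the same interval in both arms. The only vaccination-specific table covers the first 4 hours. In addition, the treatment-emergent flag could be programmed from either of two milestones, which for a control patient lie weeks apart. Finally, if Intuvax delayed progression, its arm would be observed for AEs longer, and crude counts could make a benefit look like added toxicity.

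**Working it through.** **1. The plan's own figure.** Protocol 9.1.1 says that vaccination delays nephrectomy by 14 to 20 days. The doses are "14 days (± 3 days) after Vacc1 Visit" apart, that is 11 to 17 days, and surgery follows at least 3 days later. 11 + 3 = 14 and 17 + 3 = 20, so the figure reproduces.

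**2. Length of the pre-treatment period under SAP 6.3.10.**
- Vaccine arm: "Vacc1 Visit to be done within 28 days after Screening"; the flow chart gives Day 2-28. From Day 1 this is 2 − 1 = 1 to 28 − 1 = 27 days.
- Controls: nephrectomy by Day 63 at the latest, so up to 63 − 1 = 62 days.
- As shares of the 78-week schedule (78 × 7 = 546 days): 27/546 = 4.9% and 62/546 = 11.4%.

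These are maxima. If first vaccination falls on the day a control would have had surgery, as the stated delay implies, the two periods are about equally long. The lasting difference is in content: first vaccination to nephrectomy, 14 days at least (11 + 3) and 61 at most (63 − 2), lies after the vaccine arm's pre-treatment period, while all of controls' pre-surgical time lies within theirs.

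**3. The two cut-offs for a control patient.** Sunitinib starts 5 to 8 weeks after nephrectomy (Protocol 7.2.1.5), that is 35 to 56 days. First study drug can therefore be as late as 62 + 56 = 118 days after Day 1 (118/546 = 21.6%). An AE that starts and stops between nephrectomy and sunitinib start compares as follows:

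| Rule | Control | Vaccine arm |
|---|---|---|
| SAP 6.3.10 pre-treatment period | outside it | outside it |
| SAP 6.6, start date missing | pre-treatment | not pre-treatment |
| Complete dates | flag not defined | flag not defined |

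The SAP 6.6 bullet has a narrow reach. That section imputes a start date when only the day or month is unknown, so the bullet needs an unknown year and a stop date before first study drug.

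For some patients first study drug is late or absent. SAP 4.1 says that before protocol version 4.0 intermediate-risk patients started sunitinib only after confirmed progression, and SAP 6.3.6 says some never started. For controls of that kind the SAP 6.6 milestone does not work.

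**4. Time observed.** Scheduled AE collection ends 78 ± 2 weeks after Screening in both arms (Protocol 7.2.1.7). To show what unequal progression could do, assume an exponential time to end of AE collection with rate λ, capped at 18 months. Mean time observed = (1 − e^(−18λ))/λ, with λ = ln 2/median in controls and HR × λ in the vaccine arm. The medians and hazard ratios are assumptions.

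| Control median (months) | Mean time, controls (months) | Time ratio, HR 1.0 | HR 0.8 | HR 0.6 |
|---|---|---|---|---|
| 6 | 7.6 | 1.00 | 1.16 | 1.36 |
| 9 | 9.7 | 1.00 | 1.12 | 1.25 |
| 12 | 11.2 | 1.00 | 1.09 | 1.20 |

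At an equal AE rate, event counts per patient scale with this ratio. The share of patients with at least one event moves less. With an AE hazard r = 0.05 per month in both arms and a 9-month median, the share is r/(r + λ) × (1 − e^(−18(r + λ))). This gives 35.4% in controls against 38.8% (HR 0.8) or 42.8% (HR 0.6), with no true difference in hazard.

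**The case against.** The strongest reply is that the arm-specific cut-off marks each arm's first study intervention, vaccination or surgery, which is a reasonable choice. The main tables (overall, by system organ class and preferred term, serious, by CTCAE grade) do not use it. They start at Screening in both arms, the pre-treatment summary is additional, and the treatment-emergent flag is planned for listings only. All of that stands, and it limits the point to the period-based tables and the flag.

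A reader might infer three stronger things that the documents do not support:
- *Surgical AEs count as on-treatment only in the vaccine arm.* Under SAP 6.3.10 they fall outside the pre-treatment period in both arms. The asymmetry arises only under SAP 6.6, which covers incomplete dates. The 35 to 56 days are the length of an interval, not a number of misclassified events.
- *Control AEs after surgery are lost.* They appear in the overall tables.
- *The 14 to 20 day delay gives the vaccine arm longer observation.* The schedule is counted from Screening, so the delay moves surgery within the same window. It lengthens the pre-surgical phase, not the scheduled total.

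The plan also gives some context: sunitinib duration by arm (SAP 6.3.8) and patients by visit (table 14.1.3). Neither is used as a denominator for AEs. The title of table 14.3.1.11 names no arm, so it could be run for both, but the text of SAP 6.3.10 confines that period to unvaccinated patients.

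**Conclusion.** The point holds for the period-based AE summaries, the treatment-emergent flag and the missing time denominator. It does not hold for the overall AE tables. By the schedule, the pre-treatment periods can differ by as much as 27 against 62 days but may be about equal in practice. The cut-offs in SAP 6.3.10 and 6.6 disagree for controls over the 35 to 56 days between nephrectomy and sunitinib start; the written 6.6 rule will touch few AEs, while the undefined flag for complete dates could touch more.

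Any imbalance in time observed depends on progression, death and withdrawal, which the documents do not quantify. The ratios of about 1.1-1.2 (HR 0.8) and 1.2-1.4 (HR 0.6) rest on assumed inputs, and with equal progression the ratio is 1. The trial is exploratory and its AE analyses are descriptive, so this is a cheap improvement and not a flaw that threatens the trial's conclusions.

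**What to change.** 1. Define treatment-emergent once, for complete and incomplete dates. One simple way is to keep the SAP 6.3.10 milestones and have SAP 6.6 refer to them in place of first study drug. State also which visit the Week 12 limit in SAP 6.6 means.
2. Tabulate AEs in both arms by the same four phases: Screening to randomisation, randomisation to nephrectomy, nephrectomy to sunitinib start, and sunitinib start to End-of-Study.
3. Beside the counts, give patient-months and events per patient-month for each phase. SAEs can be collected beyond End-of-Study, up to 30 days after the last dose, so state their end of observation separately.
4. For patients who never started sunitinib, end the post-nephrectomy phase at End-of-Study. Show intermediate-risk patients enrolled before protocol version 4.0 with delayed or no sunitinib separately, or in a sensitivity table.

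Everything uses dates already collected, and nothing in trial conduct changes. The cost is some programming and more tables, with sparse cells in a trial of about 90 patients randomised 2:1.
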